**Lay Summary**

We propose a single-blinded, randomized-controlled, clinical trial to evaluate the impact of an innovative model of home-based palliative care on outcomes for patients with advanced dementia and their caregivers. 250 subjects (125 patients, 125 caregivers) will be enrolled from across the Mount Sinai Health System and randomized to receive the home-based palliative care program or usual care. Intervention patients will be cared for by a pyramid of palliative care focused providers, the core of which comprises specially trained community health workers, social workers, and registered nurses. These providers are supported by a palliative care advanced practice nurse and physician. All visits will be done by video or telephone from 3/19/20 due to the ongoing risk of transmission of COVID-19. Usual care patients will have the results of their baseline interview shared with their Mount Sinai provider. Additionally, caregivers in the usual care arm will receive training from a health coach on a health issue identified as important to them (e.g., smoking cessation, healthy eating). This is a kind of attention control. of this intervention on meaningful outcomes for patients, caregivers, and the health system. Outcomes are symptom control and quality of life in persons with dementia; caregiver burden; caregiver satisfaction with care; patient days in the hospital and ED visits. In exploratory analyses we will also determine if the intervention decreases costs of healthcare. Outcomes will be ascertained through interviews with caregivers, chart abstraction from the medical record, and the Mount Sinai Data Warehouse.

**IF Number**

IF2478054

## 2. Summary - Setup

Funding Has Been Requested / Obtained	Yes
Application Type	Request to Rely on Mount Sinai IRB
Research Involves	Prospective Study ONLY
Consenting Participants	Yes
Requesting Waiver or Alteration of Informed Consent for Any Procedures	No
Humanitarian Use Device (HUD) Used Exclusively in the Course of Medical Practice	No
Use of an Investigational Device to Evaluate Its Safety or Effectiveness	No
Banking Specimens for Future Research	No
Cancer Related Research that Requires Approval from the Protocol Review and Monitoring Committee (PRMC).	No

***Is this Cancer Related Research? Cancer Related Research is defined as research that has cancer endpoints or has a cancer population as part of or all of its targeted population. This includes protocols studying patients with cancer or those at risk for cancer.***

Clinical Trial	No
----------------	----

***\* A prospective biomedical or behavioral research study of human subjects that is designed to answer specific questions about biomedical or behavioral interventions (drugs, treatments, devices, or new ways of using known drugs, treatments, or devices).***

***\* Used to determine whether new biomedical or behavioral interventions are safe, efficacious, and effective.***

Drugs / Biologics	No
-------------------	----

***\* Drugs / Biologics That Are Not a Part of Standard Practice***

***\* Controlled Substances***

***\* Drugs / Biologics Supplied by the Research Sponsor or Purchased with Study Funds***

***Ionizing Radiation for imaging or therapy, including X-Ray, Fluoroscopy, CT, Nuclear Medicine, PET andor Radiation Therapy:***

* Purely for standard of care:	No
* In frequency or intensity that exceeds what is necessary for standard of care:	No

Hazardous Materials	No
---------------------	----

***\* Recombinant DNA***

***\* Viral Vectors***

**\* *Plasmids***

**\* *Bacterial Artificial Chromosomes***

**\* *Toxic Chemicals, Potentially Toxic Medications, Carcinogens***

**\* *Autologous Cell Lines***

**Request Use of Clinical Research      No**  
**Unit Resources**

### **3. Summary - Background**

#### **Objectives**

The objective of this study is to determine whether a new home based palliative care program for patients with advanced dementia: 1) Improves overall symptom control and quality of life in patients with dementia; 2) Reduces caregiver burden, increases caregiver satisfaction, reduces caregiver depression; and 3) Reduces healthcare utilization (number of hospital admissions, days in hospital, emergency department visits) and increases days at home.

#### **Background**

Comprehensive case management programs for people with dementia and their caregivers have traditionally been clinic-based. In recent years, programs have been developed for care delivery in the home for patients with dementia, but these models focus on patient monitoring, care coordination, and caregiver support through the use of clinical and/or non-clinical coordinators. Each of the programs has had some elements of a palliative care approach, but none have been intentionally designed to provide comprehensive home-based palliative care using a team as novel as we are proposing. Our model is tailored to the needs of patients with advanced dementia and focuses on the core palliative care concepts of symptom control, caregiver support, better aligning treatments to goals and preferences, and assuring appropriate care plans to keep patients at home if this is consistent with their preferences. In addition, there is a national shortage of physicians and nurse practitioners with specialty-level training in the fields of palliative care and geriatrics. Our model is particularly innovative in that it will create a cadre of community health workers (CHWs), social workers (SWs), and registered nurses (RNs) to work with dementia patients and their caregivers. The integration of the lower-cost, more community-based CHWs within a comprehensive palliative care team builds on their effectiveness in chronic disease management while simultaneously helping to solve issues of workforce shortage.

#### **Primary and Secondary Study Endpoints**

1. Patient symptoms and quality of life (co-primary endpoints). Measured using Symptom Management at the End-of-Life in Dementia (SM-EOLD) and Quality of Life in Alzheimer's Disease (QOL-AD) respectively. Measured at baseline, 3 months, 6 months.
2. Caregiver burden, satisfaction with care, and depression. Measured using Zarit Burden Inventory, FAMCARE-10, and Patient Health Questionnaire 9 (PHQ-9) respectively. Measured at baseline, 3 months, 6 months. We will also study the effect of the intervention on caregiver self-efficacy, using the revised scale for caregiving self-efficacy.
3. Healthcare utilization: from the data warehouse as well as using the Resource Use Instrument (RUI) collected through interviews with patients. Healthcare cost: measured through the Mount Sinai Data Warehouse.

Study duration is 6 months.

**Protocol Was Already Approved** No  
by the Icahn School of Medicine at  
Mount Sinai (ISMMS) Institutional  
Review Board (IRB) Under a  
Different Principal Investigator

**Protocol Was Previously Submitted** No  
to an External(non-ISMMS) IRB

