### **Procedures for Investigator to Withdraw Subjects**

1. Death of patient (caregiver will be withdrawn)
2. No available caregiver
3. Transition to long term care (patients and caregivers)
4. Transition to skilled nursing facility for longer than 30 days (patients and caregivers)
5. Inpatient hospitalization for longer than 30 days (patients and caregivers)
6. Relocation of patient outside of Manhattan
7. Safety of clinical team cannot be assured
8. Study stopped
9. Principal Investigator deems it to be in the subject's best interest
10. The subject withdraws permission to use their PHI for research

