#### **All dyads - data collection**

For dyads in both arms, there will be an interview undertaken at baseline, 3 months, and 6 months. This will be undertaken either in person (at the dyad's home or a Mount Sinai facility) or over the telephone. At all times confidentiality will be assured. These interviews will last around 30 minutes.

Any concerns that arise during interview will be shared with the patient's treating provider (either the palliative care team or for control patients, their PCP).

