### **Description of the Source Records that Will Be Used to Collect Data About Subjects**

1. EMR - we will abstract data from the patient's EMR at baseline, 3 months, and 6 months and after every hospitalization.
2. Mount Sinai Data Warehouse. We will request data on utilization and costs of care from the data warehouse on enrolled subjects.
3. Claims databases. We will request claims data for enrolled patients (using the same variables as the data warehouse) to study the impact of the intervention on utilization and costs.

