**Description of Data that Will Be Collected Including Long-Term Follow-Up**

1. Patient/ proxy and caregiver reported data - through interviews.

Data to be collected will include: (i) patient demographics; (ii) symptoms; (iii) quality of life; (iv) resource use; (v) physical function; (vi) agitation; (vii) care preferences; (viii) financial burden.

We will obtain information from the patient's caregiver (as a subject) about: (i) caregiver demographics; (ii) caregiver health; (iii) caregiver function; (iv) caregiver burden; (v) caregiver depression; (vi) caregiver satisfaction; (vii) caregiver self-efficacy.

2. Data warehouse/ claims database (ClaimsStar)

We will abstract data from the data warehouse and the claims database on utilization, diagnoses, and costs of care.

**Research Requires HIV Testing**      No

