**Description of Health Information That Will Be Viewed, Recorded, or Generated**

Data warehouse query (screening purposes):

1. Patient name
2. Patient MRN
3. All encounters within the Mount Sinai system in quarter of request and 12 months prior:
  - a. Encounter ID
  - b. Dates of encounter (admit and discharge)
  - c. Encounter type (e.g., outpatient, inpatient)
  - d. Discharge disposition
  - e. Discharge location to
  - f. ICD10 code and diagnosis description
  - g. ICU admission
  - h. Encounter site
  - i. Provider
  - j. Payer
  - k. Wheelchair order
  - l. Hospital bed order
4. Patient zipcode
5. Patient date of birth

From this information, we will generate a list of patients with a diagnosis of dementia. We will then review the charts of these patients to determine potential eligibility.

Chart review (screening purposes):

1. Name, MRN, date of birth
2. Physician note of behavioral or psychological symptoms of dementia (yes/no)
3. Psychotropic medication (yes/no; type)
4. Documented MMSE < 20 in past 6 months (yes/no).
5. Evidence of any of the following: needs assistance with dressing, bathing, toileting; urinary or fecal incontinence; weight loss; dysphagia/ aspiration; immobility; loss of ability to communicate (yes/no; checkbox for each)

Interviews (enrolled subjects):

Patients:

Demographics (study team)  
Symptoms (SM-EOLD) - standardized  
Quality of life (QOL-AD) - standardized  
Function (KATZ ADL and IADL) - standardized  
Resource use (RUI) - standardized  
Care preferences - study team  
Cohen Mansfield Agitation Inventory - standardized  
Financial burden - study team  
Neuropsychiatric Inventory Questionnaire - standardized

Caregivers:

Caregiver demographics (study team)  
Caregiver burden (Zarit Burden Inventory) - standardized  
Caregiver depression (PHQ-9) - standardized  
Caregiver satisfaction with care (FAMCARE-10) - standardized  
Caregiver self efficacy (revised scale for caregiving self-efficacy) - standardized  
Caregiver comorbidities (KATZ) - standardized

Chart reviews at baseline and follow up (enrolled subjects)

1. Medications (name, dose)
2. Hospitalizations and ED visits in past 12 months (yes/ no/ number)
3. Advance care planning documentation
4. Receipt of any of the following: (i) IV fluids (ii) IV antibiotics (iii) PEG (iv) Intubation (v) CPR

Data warehouse (enrolled subjects):

All encounters in the Sinai health system from enrollment until study termination:

1. Patient name
2. Patient MRN

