## Statistical Analysis Plan

ID: GCO 17-02787

Palliative Care at Home for Dementia

NCT03798327

[name] – PI

March 2020

**1. Overview.** For continuous outcomes, we will compare the changes from baseline across multiple repeated measurement points between different treatment groups using mixed linear model to control for within-subject effect.

**2. Descriptive Study.** We will characterize subjects with regard to baseline and follow-up measures and change between assessments. Descriptive statistics of demographics, disease-related and treatment related variables will be calculated and compared at baseline between the treatment group and control group. T-test, Chi-square, Fishers exact test will be used as appropriate.

**3. For the primary outcomes measures,** we will examine changes in outcomes over time. As possible, we will test the differences in mean total scores between the main predictors of treatment groups (intervention vs. control) and time (baseline, 3 months, and 6 months), and the interaction term between these two predictors, which indicates the variation of difference of outcome trajectories between interventions and controls by baseline scores.

**4. Utilization.** We will measure counts of utilization including, as applicable, those related to the number of hospital admissions, number of hospital days, number of days out of hospital, and ED usage. We will perform simple counts followed by descriptive statistics between the two groups.

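### RUI counts omit the interval from the last interview to death or exit; SAP section 4 should fill it from the planned claims and report events per covered patient-month

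*Protocol*

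**What the plan says.** Item 3 of the protocol's Primary and Secondary Study Endpoints takes utilization "from the data warehouse as well as using the Resource Use Instrument (RUI) collected through interviews with patients". The RUI belongs to the interview battery: section 20, Data - Collection, lists "Resource use (RUI) - standardized" among the interview instruments. Section 12 describes the interview material as "Patient/ proxy and caregiver reported data - through interviews" and says that for both arms "there will be an interview undertaken at baseline, 3 months, and 6 months". Item 3 gives no time points of its own, so the RUI schedule is read from this general rule.

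The withdrawal list in section 9 opens with "Death of patient (caregiver will be withdrawn" and includes "Inpatient hospitalization for longer than 30 days (patients and caregivers". It also covers long-term care, skilled nursing stays over 30 days, relocation and loss of the caregiver. Section 24 repeats most of these. After a voluntary withdrawal, only the patient's routine-care records may be collected, with permission. Neither document describes an interview at exit or after death.

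Other sources exist. Section 12 plans record abstraction at each interview time and after each hospitalization, a warehouse request, and claims: "We will request claims data for enrolled patients (using the same variables as the data warehouse". Section 20 adds follow-up chart review of hospitalizations and ED visits.

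On analysis, SAP section 4 says "We will perform simple counts followed by descriptive statistics between the two groups". It does not mention the RUI, exits, time at risk or which source prevails.

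**The concern.** The RUI is the interview-based source and is not confined to Mount Sinai encounters. For a completer, two post-baseline interviews can cover the full 6 months. A patient who dies in month 5 has RUI data for months 0 to 3 only, and one who dies in month 2 has none after baseline. The missing time is not time after exit: the patient was alive, enrolled and under the assigned care.

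One case needs no assumed rate. Hospital days are a stated outcome, and a hospital stay over 30 days ends participation. If such a stay begins after one interview and triggers withdrawal before the next, no scheduled RUI asks about it. Some of the longest stays can therefore drop out of the RUI count through the exit rule.

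RUI coverage is thus fullest for completers and stops short for those who die or leave, a period when use may well be high. If exits differ between arms, a raw RUI count differs partly because coverage differs.

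**Working it through.** The plan gives no figure to reproduce: neither document states a death rate, exit rate or utilization rate. What follows is illustration.

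**From the documents:** interviews at 0, 3 and 6 months; participation of 6 months.

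**Assumed:** each RUI covers the time since the previous interview; exits are uniform over 6 months; a share p of patients exits, p from 0.10 to 0.40; the event rate is 1 per month, multiplied by k = 1, 3 or 5 in the last 3 months before exit.

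**Time.** Mean followed time of an exiting patient is 3.0 months. The gap (exit time minus last interview) averages 1.5 months, so 1.5/3.0 = 50% of that time is uncovered. Half of those who exit leave before month 3 and have no post-baseline RUI. The uncovered share of all followed time is 1.5p / (6 - 3p):

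- p = 0.10: 0.15/5.7 = 2.6%
- p = 0.20: 0.30/5.4 = 5.6%
- p = 0.30: 0.45/5.1 = 8.8%
- p = 0.40: 0.60/4.8 = 12.5%

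**Events per exiting patient.** True total = 2.25k + 0.75; RUI captures 0.75k + 0.75; missed = 1.5k.

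| k | true | captured | missed | share missed |
|---|---|---|---|---|
| 1 | 3.0 | 1.5 | 1.5 | 50% |
| 3 | 7.5 | 3.0 | 4.5 | 60% |
| 5 | 12.0 | 4.5 | 7.5 | 62.5% |

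As a share of all trial events, 1.5kp / [6(1 - p) + p(2.25k + 0.75)]: at k = 3, from 0.45/6.15 = 7% (p = 0.10) to 1.80/6.60 = 27% (p = 0.40); at k = 5, from 0.75/6.60 = 11% to 3.00/8.40 = 36%.

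**RUI-only count, 20% exits on intervention against 30% on control (assumed).** Events per randomized patient:

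| k | true ratio of counts | RUI-only ratio |
|---|---|---|
| 1 | 5.40/5.10 = 1.059 | 5.10/4.65 = 1.097 |
| 3 | 6.30/6.45 = 0.977 | 5.40/5.10 = 1.059 |
| 5 | 7.20/7.80 = 0.923 | 5.70/5.55 = 1.027 |

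**Sources combined, no claims at all.** Let s be the share of events outside Mount Sinai; only these are then missed in the gap.

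- k = 3: ratio = (6.30 - 0.90s)/(6.45 - 1.35s). It reaches 1 when 0.45s = 0.15, so s = 33%.
- k = 5: ratio = (7.20 - 1.50s)/(7.80 - 2.25s). It reaches 1 when 0.75s = 0.60, so s = 80%.
- At s = 20% (assumed): 6.12/6.18 = 0.99 against a true 0.98, and 6.90/7.35 = 0.94 against a true 0.92.

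**Does a covered-time denominator suffice for an RUI-only count?** Covered months per patient are 6(1 - p) + 1.5p: 5.10 and 4.65. Followed months are 5.40 and 5.10.

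- k = 3: covered-time rate ratio (5.40/5.10)/(5.10/4.65) = 0.97; true rate ratio (6.30/5.40)/(6.45/5.10) = 0.92.
- k = 5: (5.70/5.10)/(5.55/4.65) = 0.94; true (7.20/5.40)/(7.80/5.10) = 0.87.

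The denominator removes the apparent increase but not all of the distortion, because the missing time is the high-use time. Filling the interval matters as well.

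**The case against.** The strongest reply is that utilization does not rest on the RUI. Record abstraction follows every hospitalization, chart review at follow-up asks about admissions and ED visits, the warehouse runs from enrollment to study termination, and claims are requested to study utilization and costs. This stands. A reader might infer that use before death is lost to the trial; the documents do not support that. It stands with a limit: the warehouse holds Mount Sinai encounters only, and claims are not named in the endpoint section or among the data collection sources in section 20. No text says that claims fill RUI gaps.

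A second reply is that no stand-alone RUI comparison is planned. The endpoint pairs the RUI with the warehouse, and SAP section 4 does not name it. This also stands. A reader might infer that the trial's utilization comparison would reverse direction; that has been shown only for an RUI-only count. Even there the exit imbalance is assumed, and the model has no treatment effect on event rates: its true ratios differ from 1 only because exits differ.

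Third, the instrument file and funding proposal are not among the documents, and section 9 mentions a termination form whose content is not shown. A form for use at exit or after death cannot be ruled out. The record supports saying that none is described.

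Finally, this is a non-primary outcome, summarized descriptively in a trial that calls itself a pilot. That limits the weight of the point without removing it.

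**Conclusion.** The point holds for the RUI as a source. As described, its counts stop at the last completed interview and are systematically short for patients who die or exit, and SAP section 4 has no denominator or source rule to allow for that. For the utilization outcome as a whole, the real loss is mainly care outside Mount Sinai in that window where claims are not obtained or are incomplete.

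The size depends on unstated exit rates, exit timing, use before exit and the share of care given elsewhere, so the percentages above show a range and do not predict the result. The co-primary endpoints are untouched. It is worth acting on because the remedy uses data already planned.

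**What to change.** In SAP section 4:

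1. For each patient who dies or exits, fill the interval from the last completed RUI to the exit date from the claims extract already planned in protocol section 12, with warehouse and record data for Mount Sinai encounters.
2. Count events only over intervals covered by a completed RUI or by claims. Where neither exists, list any Mount Sinai events separately.
3. Report events per covered patient-month by arm, with covered months shown, instead of simple counts alone.

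This costs some SAP wording and analyst time, with no new participant contact. It does depend on claims being obtained.

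Optionally, a short protocol amendment to section 12 could add one brief RUI-only telephone call to the caregiver at exit, made by the existing coordinators and covering the time since the last interview. The downside is contact with a caregiver who may be recently bereaved, so this is the sponsor's choice. The withdrawal rules do not change.

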**6. Subjects - Enrollment**

Site Name	Icahn School of Medicine at Mount Sinai
Subjects To Be Enrolled	60
Site Name	Mount Sinai Beth Israel
Subjects To Be Enrolled	40
Site Name	The Mount Sinai Hospital
Subjects To Be Enrolled	90
Site Name	Mount Sinai St. Luke's
Subjects To Be Enrolled	40
Site Name	Mount Sinai West
Subjects To Be Enrolled	20
Total Number of Subjects to be Enrolled Across All Listed Sites Above (Auto Populated)	250

## **7. Subjects - Setting and Resources**

**Setting of Human Research**

Faculty Practice Associates, Emergency Department, Internal Medicine Associates, Other

**Specify Other Setting of Human Research**

Patient home - we enroll subjects in their home as well as conducting follow up interviews in their home. This has been specified elsewhere in the previously approved protocol. This is because without home enrollments, many of the subjects would not be able to access the study.

Note - from 3/19/2020, we will no longer plan to conduct home enrollments, due to the risk of transmission to patients from COVID-19. Instead, we will transition to using an electronic consent protocol. Baseline and follow up interviews will be conducted telephonically in all cases.

**Total Number of Subjects Needed 250  
To Complete Study**

**Feasibility of Meeting Recruitment Goals**

Our enrollment target is 4 dyads per month (50 dyads per year). Through preliminary analysis, we have identified around 1700 patients per quarter who have a diagnosis of dementia, and around 60% of these are in the advanced stages. To meet our enrollment target, we would have to enroll 5% of these patients. We are therefore confident of reaching our target.

**Facilities To Be Used for Conducting Research**

The Department of Geriatrics and Palliative Medicine is consistently ranked as one of the top programs in the nation. The Department provides expert care for the most frail and complex patients; conducts research in aging with an emphasis on medical decision-making and palliative medicine; and teaches geriatrics and palliative medicine to medical students, house staff, attending physicians, and other health professionals. The principal investigator is [name], a geriatrician and palliative care physician who has experience in administering large clinical trials, as is demonstrated by his multi-center trial that enrolled more than 550 patients across 6 sites. [name] is a geriatrician and palliative care physician whose research has focused on enhancing decision making for patients with dementia and developing health system interventions to improve outcomes. [name] is a geriatrician, palliative care physician, and a health services researcher who will lead the use of models to identify eligible patients based on diagnostic codes from the electronic health record. [name] is a geriatrician and the Director of Mount Sinai Visiting Doctors as well as Clinical Director of Mount Sinai Hospital at Home. She has expertise in the delivery of clinical models that provide care to complex older adults living in the community.

---

**Multi-Center Study** No

---

**Community-Based Participant Research Study** No

